APPENDIX I SAMPLE SAS CODE IN STATISTICAL ANALYSIS

1) Sample Code for Efficacy Analysis

The logistic regression will be used to analyze all efficacy endpoints relating to proportions

The following is an example of the SAS codes used to perform the analysis of this LOGISTIC model.

* SAS Codes: *LOGISTIC* model

* Variables in the model:

* resp = proportion of patients who have converted from AF within 90 mn from the start of infusion

* Duration of current AF episode = Dur

*trtp = treatment planned

*****;

```
proc logistic data=eff descending;
class trtp (param=ref ref='Placebo');
model resp (event="Yes")= trtp dur;
```

```
contrast 'Pairwise' trt 1 -1 0 /estimate=exp;
contrast 'Pairwise' trt 1 0 -1 /estimate=exp;
```

```
ods output Contrastestimate=est;
run;
```

A Kaplan-Meier analysis was used for time to conversion. An example of the SAS code to perform this analysis is below.

* SAS Code: Kaplan-Meier Analysis

* Variables in the model:

* timeconv = The time to conversion from AF from start of infusion

* Censor = censor variable (0=patients with conversion, 1=censored patients, no pharmacological conversion)

*trtp = treatment planned

*****;

```
proc lifetest data=dataset plot;
```

This document is confidential.

```
time timeconv*censor(1);
strata trtp/ test=(logrank) diff=control('Placebo');
ods output quartiles/quartile
run;
```

2) Sample Code for graph

```
*****
```

* SAS Code: Graph Concentration response relationship:

QTcF versus AP30663 plasma concentrations

* PCTRESN = Plasma concentration

* AVAL = QTcF

```
*****
```

```
proc sgplot data=PKPD;
reg x=PCSTRESN y=AVAL /CLM alpha=.05;
refline 0/axis=y;
label PCSTRESN="Plasma concentration (unit)";
run;
```

This document is confidential.

AP30663_2001_SAP_Text_4.0_20Feb2023

Final Audit Report

2023-02-20

Created: 2023-02-20

By: PPD [REDACTED]

Status: Signed

Transaction ID: PPD [REDACTED]

"AP30663_2001_SAP_Text_4.0_20Feb2023" History

-  Document created by PPD [REDACTED]
2023-02-20 - 2:01:32 PM GMT- IP address: PPD [REDACTED]
-  Signer PPD [REDACTED] entered name at signing as PPD [REDACTED]
2023-02-20 - 2:04:32 PM GMT- IP address: PPD [REDACTED]
-  PPD [REDACTED] verified identity with Adobe Acrobat Sign authentication
2023-02-20 - 2:04:34 PM GMT
-  Document e-signed by PPD [REDACTED]
Signing reason: I am the author
Signature Date: 2023-02-20 - 2:04:34 PM GMT - Time Source: server- IP address: PPD [REDACTED]
-  Document emailed to PPD [REDACTED] for signature

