8.1. Primary Efficacy Endpoint and Analysis

The primary efficacy endpoint is defined as the proportion of patients who have converted from AF within 90 min from the start of infusion, and subsequently have no AF recurrence within 1 min of conversion from AF.

For the analysis of the primary endpoint (proportion of patients who have cardioversion within 90 min from the start of infusion) a Bayesian model will be utilised. The prior probability of success at a dose, d , is modelled with a $P_d \sim \text{Beta}(1,1)$ prior (uniform) for each dose. Across both Parts 1 and 2 of the study, the potential doses (arms) in the trial are $d = 0$ (placebo), 2, 3, 4, 5, and 6 (all mg/kg dose units).

Let X_d be the number of successes and N_d be the number of observations at dose d . The posterior distribution is calculated for each dose independently using a Beta posterior distribution,

$$P_d \sim \text{Beta}(1 + X_d, 1 + N_d - X_d).$$

The adaptive design utilises the probability that the response rate at a dose is greater than a 65% success rate. This is ($P_d > 0.65$), for each dose d .

This modelling will occur for each interim analysis, and at the final analysis as primary method. At the conclusion of the study, each AP30663 dose will be considered to be superior to placebo, if the posterior probability of AP30663 dose having a higher success rate than placebo is greater than 0.95.

Further to the above, the primary endpoint will also be analysed by means of a logistic regression model. The model will include treatment and duration of current AF episode.

Duration of current AF episode (in hours) = date/time of randomisation – date/time of AF symptom onset

If no time of AF symptom onset is available, '00:00' will be used for the calculation of the duration.

All statistical tests will be 2-sided and conducted at the 5% significance level. All presented confidence intervals will be 2-sided 95% confidence intervals.

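### Ordinary maximum-likelihood logistic regression is the only inferential method for IRAF and sinus rhythm, where empty or full arms are likely, and the SAP names no method for that case

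*SAP*

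**What the plan says.** For the primary endpoint, SAP 8.1 makes the independent Beta-binomial model the main analysis: "This modelling will occur for each interim analysis, and at the final analysis as primary method". The logistic model comes second: "Further to the above, the primary endpoint will also be analysed by means of a logistic regression model". Its terms are fixed: "The model will include treatment and duration of current AF episode".

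SAP 8.2.2 applies the same model to IRAF after drug or DC cardioversion, and again to IRAF after drug conversion only. SAP 8.2.3 applies it to SR at 3 h, 24 h and 30 days. Both sections also present the proportions by treatment, but the logistic model is the only inferential method they name.

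Appendix I states the general rule, "The logistic regression will be used to analyze all efficacy endpoints relating to proportions", and gives sample code beginning "proc logistic data=eff descending", with placebo as reference level ("class trtp (param=ref ref='Placebo"). The MODEL statement has no Firth option and no profile-likelihood request, and there is no EXACT statement. The code exports estimates from CONTRAST statements. Neither document says what to do if the model separates or fails to converge. SAP Section 16 marks the logistic tables for conversion (14.2.1.1.3) and SR (14.2.2.3.1) for delivery at the interim analyses.

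**The concern.** If no patient, or every patient, in an arm has the event, the likelihood for that arm's coefficient has no finite maximum. Software then prints whatever value the optimiser stopped at, with a huge standard error. The position of the empty cell matters:

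- In an active arm, it spoils that dose's comparison only.
- In placebo, the reference, it spoils every dose-versus-placebo odds ratio.

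The arms are small. Part 1 has up to 18 per arm. A Part 2 cohort of 18 gives 12 active and 6 placebo with one dose open, or 6 per arm with two doses open. Stability of rhythm control is a stated secondary objective, and IRAF is its endpoint. If its only model gives no usable estimate, a substitute has to be chosen after unblinding, which one sentence in the SAP would avoid.

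**Working it through.** The documents state no separation probability, so there is no figure of theirs to reproduce.

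**Inputs.** The final data of Example 1 (protocol 17.3): placebo 6/42, 3 mg/kg 10/18, 4 mg/kg 8/12, 5 mg/kg 28/36. Relapse and SR rates are assumptions, taken equal in all arms. Arms are independent, so P(at least one degenerate arm) = 1 − Π(1 − D), where D is the chance that a given arm is degenerate.

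**IRAF after drug conversion only.** With arm size n, conversion rate p and relapse rate q, and converters as the denominator (the SAP does not state it):

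D = (1 − pq)^n + (1 − p(1 − q))^n − (1 − p)^n

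The first term, no relapse in the arm, dominates: for placebo at q = 5% it is 0.740 of 0.741. Counting all patients instead of converters would therefore change little.

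| q | placebo | 3 mg/kg | 4 mg/kg | 5 mg/kg | any arm |
|---|---|---|---|---|---|
| 5% | 0.741 | 0.602 | 0.666 | 0.240 | 97% |
| 10% | 0.548 | 0.357 | 0.437 | 0.054 | 85% |
| 20% | 0.300 | 0.120 | 0.180 | 0.002 | 50% |

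For the first row: 1 − 0.259 × 0.398 × 0.334 × 0.760 = 0.974.

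**IRAF after drug or DC conversion.** Assuming everyone is cardioverted, D = (1 − q)^n + q^n.

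| q | placebo | 3 mg/kg | 4 mg/kg | 5 mg/kg | any arm |
|---|---|---|---|---|---|
| 5% | 0.116 | 0.397 | 0.540 | 0.158 | 79% |
| 10% | 0.012 | 0.150 | 0.282 | 0.022 | 41% |
| 20% | <0.001 | 0.018 | 0.069 | <0.001 | 9% |

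**SR.** The same formula with q as the SR rate is symmetric, so SR of 80%, 90% and 95% gives 9%, 41% and 79%. High rates are plausible because protocol 8.4.8.2 sends non-converters to DC cardioversion, but no rate is given.

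**Primary endpoint, example rates.** D = (1 − p)^n + p^n.

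- Example 1, final: 1 − (1 − 0.0015)(1 − 0.00003)(1 − 0.0077)(1 − 0.0001) = 0.9%. Examples 2, 3 and 4 give 1.3%, 0.4% and 1.2% (reading Example 4's final active arms as 4/12, 13/18 and 24/36).
- Part 1 interim, empty placebo arm at p = 0.11: 0.89^18 = 12%.
- First Part 2 interim of Example 4 (placebo 4/24, doses 3/6 and 4/6): 1 − (1 − 0.013)(1 − 0.031)(1 − 0.089) = 13%.
- Assumed lower placebo rates, n = 42: 0.95^42 = 12% and 0.97^42 = 28%.

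**What Firth's method returns** (treatment-only fits). For two arms without a covariate it amounts to adding 0.5 to each cell.

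- 0/18 versus 10/18: maximum likelihood diverges. Firth gives (10.5/8.5)/(0.5/18.5) = 45.7, with a profile interval of 4.9 to about 6,100.
- 6/42 versus 10/18: maximum likelihood gives (10/8)/(6/36) = 7.5. Firth gives (10.5/8.5)/(6.5/36.5) = 6.9.

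**The case against.** A reader might infer that the supportive analysis of conversion will often fail, and will fail just when the drug works best. The documents do not support that. Placebo accumulates over both parts, reaching 42 in the protocol's examples, and the final example arms run up to 36 on active drug. At those rates the risk is about 1%. An empty placebo cell reflects a low placebo rate, not a large drug effect: Example 1's 6/42 versus 28/36 is a large effect with no separation. The risk becomes material at the final analysis only if true placebo conversion is well below the examples.

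Nor is the trial's conclusion at stake. The Beta posterior handles empty cells. With 0/18 versus 10/18 the posterior probability of superiority is 0.9999.

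It is also fair to say that the largest IRAF figures belong to the additional drug-only analysis, that every IRAF and SR figure rests on an assumed rate, that raw proportions will be shown regardless, and that the code is labelled an example in a proof-of-concept study. These points limit the weight of the concern. They do not remove it: the drug-or-DC endpoint still has a degenerate arm in 41% to 79% of trials at 10% to 5% relapse, and neither the SAP text nor its code offers an alternative.

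Finally, Firth's method restores a finite estimate but not information. The interval from 0/18 versus 10/18 remains extremely wide.

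**Conclusion.** The point holds for IRAF and, if SR rates are about 90% or higher, for SR. There the plan's only inferential method is likely to give at least one unusable comparison. The sizes depend on assumed relapse and SR rates common to all arms, on the Example 1 layout and, for the drug-or-DC endpoint, on everyone being cardioverted. At 20% relapse, or at 80% SR, the risk for the drug-or-DC and SR endpoints falls to 9%.

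For conversion the point is minor: about 1% at the final analysis under the example rates, and 12% to 13% at the small interims, where the logistic table is also delivered. Interim dose decisions and the final superiority statement rest on the Beta model and do not change. This is a cheap improvement the sponsor should make, not a threat to the primary result.

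**What to change.** In SAP 8.1, 8.2.2, 8.2.3 and Appendix I, state that the IRAF, SR and supportive conversion models, including the logistic tables delivered at the interims, are fitted with Firth's penalised likelihood:

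`model resp(event='Yes') = trtp dur / firth clparm=pl clodds=pl;`

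Report the profile-penalised-likelihood odds ratios and intervals from that statement. The output must change as well as the model line, because the sample code exports CONTRAST estimates, whose intervals remain Wald-based even when the model is penalised.

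The cost is a model option and a changed output table. Odds ratios shrink slightly when no cell is empty (7.5 to 6.9 in the example above), and intervals remain very wide when one is. If the sponsor prefers to keep maximum likelihood where it converges, naming Firth's method in advance as the fallback for separation would meet the main need.
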